9.1.7. Serious Adverse Events

An SAE is defined as any event that:

- Results in death
- Is immediately life-threatening
- Requires inpatient hospitalization or prolongation of existing hospitalization
- Results in persistent or significant disability/incapacity
- Is a congenital anomaly/birth defect
- Is an important medical event that may not result in death, be life-threatening, or require hospitalization but, based upon appropriate medical judgment, jeopardizes the participant or may require medical or surgical intervention to prevent one of the other outcomes listed in this definition. Examples of such medical events include allergic bronchospasm requiring intensive treatment in an emergency room or at home, blood dyscrasias or convulsions that do not result in inpatient hospitalization, or the development of drug dependency or drug abuse.

The percentage of participants with SAEs onset date within day 1-180 will be provided by dose group, by grade, outcome and causality.

The number and percentage of participants with SAE onset date within day 1-28 and within day 1-180 will be summarized by SOC, PT and causality for each dose group (any, fatal, causally related, fatal/causally related).

SAEs will be summarized and listed from the time participant signs the ICF until exit from study (up to day 180 after the study vaccine administration, day 1-180).

A data listing for all SAEs will be provided by age group, dose group and participant number.

9.1.8. Medically Attended Adverse Events

Medically attended adverse events (MAAEs) is defined as an AE that results in a visit to a medical professional. Medically attended visits are defined as telemedicine visit, physician's office visit, urgent care visit, emergency room visit, hospitalization, or death. Scheduled study visits will not be considered medically attended visits. Medically attended adverse events related

to study vaccination are to be reported from the time of first study vaccination until completion of the participant's last study-related procedure, which may include contact for safety follow-up.

The percentage of participants with MAAE onset date within day 1-180 will be provided by dose group and by grade.

All MAAEs and treatment-related MAAEs with onset date within day 1-28 and within day 1-180 will be presented in separate summary tables for each dose and age group and total by SOC and PT. All MAAEs will be presented in a data listing by age group, dose group and participant number.

MAAEs will be reported in both listings and summaries from the time participant signs the ICF until exit from study (up to day 180 after the study vaccine administration, day 1-180).

9.1.9. Adverse Events Leading to Treatment Discontinuation

Not applicable.

9.1.10. Adverse Events Leading to Study Discontinuation

Adverse events leading to study discontinuation are identified on the study disposition page of the eCRF by the AE number.

The number and percentage of participants with AE leading to discontinuation with onset date within day 1-28 will be summarized by SOC and PT for each dose group.

AEs leading to study discontinuation will be presented and a data listing will be provided by age group, dose group and participant number.

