6.1.1.2 Eliciting and Documenting Adverse Events

Adverse events will be reported throughout the study. Nonserious AEs will be reported from the time of the administration of IP until 28 days after the administration of IP; SAEs will be reported from the time the participant signs the ICF until exit from the study.

If the investigator learns of any SAE, including a death, at any time after a participant has been discharged from the study, and he/she considers the event to be reasonably related to the IP, the investigator must notify PPD Pharmacovigilance within 24 hours of learning of the event (Section 6.1.1.3.1).

At every study visit, participants will be asked a standard nonleading question to elicit any medically related changes in their well-being.

In addition to participant observations, AEs identified from any study data (eg, laboratory values, physical examination findings) or identified from review of other documents (eg, participant eDiaries) that are relevant to participant safety will be documented on the AE page in the eCRF.

As described in Section 6.1.1.1.1, participant eDiaries will be used to collect solicited AEs.

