3.1. Overall Study Design and Plan

This Phase 1 study will evaluate the safety, reactogenicity, and immunogenicity of the CV2CoV vaccine in SARS-CoV-2 seropositive healthy adult participants. The study will be conducted in 5 sequential cohorts with dose escalation from 2 μ g to 20 μ g. Each cohort will include the dose and age groups as indicated in Table 3-1. A study design schematic is provided in Figure 3-1.

A total of up to approximately 180 healthy adult participants will be enrolled, 30 per dose group. The 30 participants will be distributed between the younger (\geq 18 to <65 years old) and older (\geq 65 years old) age groups, with a minimum of 10 and a maximum of 20 participants in each age group. There will be 3 sentinel participants in each age group within each dose group. (Table 3-1).

The screening period will be up to 14 days, study vaccine administration will occur on Day 1, and participants will have approximately 180 days (6 months) of follow-up after study vaccine administration. The study will be open label.

Participants in all cohorts will be screened for eligibility up to 14 days before enrollment. Participants will receive study vaccine according to their cohort (Table 3.1-1), dose group, and age group; and study visits will proceed according to the schedule of events (SOE) provided in Appendix 15.1. Participants will be sequentially enrolled to the dose level assigned to their cohort.

Enrollment in each dose cohort and the progression from vaccination in younger to older adult participants will be staggered based on SRT data review will progress as described in protocol Section 7.8. Holding rules for dosing are described in protocol Section 5.9.

Three sentinel participants in the younger age group (Cohort 1) will be enrolled before opening enrollment to the older age group (Cohort 1).

Escalation to the next higher dose cohorts will be based on the SRT review of safety data from the same age group.

[figure not shown]
Enrollment into Cohorts 2 and 3 (8 and 12 μ g, respectively) will begin after the SRT has reviewed Days 1 to 8 safety data (including Day 8 laboratory data) from 3 sentinel participants from the previous dose cohort. Enrollment into Cohorts 4, and 5 (16 μ g, and 20 μ g, respectively), will begin after the SRT has reviewed Day 1 to 8 safety data (including Day 8 laboratory data) from all participants in the previous dose cohorts.

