5.1. Disposition

Participant disposition will be summarized by dose group for all participants. A disposition of participants includes the number and percentage of participants for the following categories: participants who were enrolled, who were vaccinated, participants who discontinued from the study (i.e., did not complete the Day 180 visit), and participants who were in the Enrolled Set, PP Set and Safety Set.

A participant may withdraw or be withdrawn from the study for any of the following reasons:

• The participant does not meet the protocol inclusion or exclusion criteria

- The participant is noncompliant with the protocol
- The participant has a serious or intolerable AE(s) that in the investigator's opinion requires withdrawal from the study
- The participant has safety laboratory results that reveal clinically significant hematological or biochemical changes from the baseline values, per investigator judgment
- The participant has symptoms or an intercurrent illness not consistent with the protocol requirements or that justify withdrawal
- The participant is lost to follow-up
- Other reasons (e.g., pregnancy, development of contraindications of use of the IP)
- The participant withdraws consent, or the investigator or sponsor decides to discontinue their participation in the study withdrawal of consent by participant or the investigator or sponsor decides to discontinue their participation in the study.

Participant status summaries will also be provided that include participants who completed each visit, participants vaccinated with study vaccine, participants who had immunogenicity results at an applicable visit, and participants who completed the study. Participant status summary will be also presented by dose and age group.

Participant disposition and discontinuation data will be presented in a listing sorted by age, dose group and participant number.

The number of participants included in each analysis set will be summarized. A listing of participants in each analysis set will also be provided by age, dose group and participant number. Participants excluded from the analysis sets will be listed with reason for exclusion(s) and sorted by age, dose group and participant number.

The primary reasons for study discontinuation include:

- AE,
- Death,
- Lost To Follow-up,
- Physician Decision,
- Pregnancy,
- Protocol Deviation,
- Site Terminated by Sponsor,
- Study Terminated by Sponsor,
- Withdrawal of Consent by Participant,

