8.4. Analysis of COVID -19 Incidence-Adverse Event of Special Interest

Proportion of participants with the following will be summarized by dose group:

- 1. Laboratory-confirmed (RT PCR) symptomatic SARS-CoV-2 infection
- 2. Laboratory-confirmed asymptomatic or symptomatic (RT-PCR or N protein seroconversion) SARS-CoV-2 infection
- 3. Laboratory-confirmed severe SARS CoV-2 infection
- 4. Medically attended visits due to laboratory-confirmed SARS-CoV-2 infection
- 5. Hospitalizations or death due to laboratory-confirmed SARS-CoV-2 infection

Frequencies and estimates of the proportion of participants with the above events from study vaccination through the end of the study will be computed by dose group.

9. Safety Analysis

Safety, tolerability, and reactogenicity will be assessed by clinical review of all relevant parameters including solicited and unsolicited AEs, SAEs, AESIs, MAAEs, AEs leading to withdrawal from study participation, safety laboratory test results, vital signs, and physical examination findings.

All safety analyses will be based on Safety Set. All safety analyses will be provided by dose group and age group unless otherwise specified.

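### The SOC/PT table in SAP 9.1.10 omits study discontinuations caused by SAEs, MAAEs or AESIs with onset after Day 28

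*SAP*

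**What the plan says.** SAP Section 9.1.10 specifies one summary of AEs leading to study discontinuation, split by dose group: "The number and percentage of participants with AE leading to discontinuation with onset date within day 1-28 will be summarized by SOC and PT". It adds a listing, with no onset limit stated: "AEs leading to study discontinuation will be presented and a data listing will be provided by age group, dose group and participant number". The events are identified by AE number from the disposition page of the eCRF.

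Other parts of the plan set the time frame:

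- Follow-up (SAP 3.1): "participants will have approximately 180 days (6 months) of follow-up after study vaccine administration".
- Discontinuation (SAP 5.1) is defined against the last visit: "participants who discontinued from the study (i.e., did not complete the Day 180 visit". AE and death are among the primary reasons listed there.
- Safety parameters (SAP Section 9, opening paragraph) include "AEs leading to withdrawal from study participation", with no Day 28 limit.
- Collection (Protocol 6.1.1.2): "Nonserious AEs will be reported from the time of the administration of IP until 28 days after the administration of IP". Footnote m of the schedule of events, in both documents, carries SAEs, MAAEs and AESIs through the whole study.
- Neighbouring tables: MAAEs are tabulated "with onset date within day 1-28 and within day 1-180" (SAP 9.1.8). AESIs (9.1.6) and SAEs (9.1.7) have the same two windows, and fatal AEs (9.1.11) run from Day 1 to Day 180.

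The SAP gives no reason for the shorter window in 9.1.10.

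**The concern.** The plan names AEs leading to withdrawal as one of the parameters for judging safety and tolerability, and it defines discontinuation by the Day 180 visit. The only table that counts such AEs by SOC and PT stops at onset on Day 28. The event classes collected after that day are serious, medically attended or of special interest, and so are plausible causes of a late withdrawal. They will be in the database and linked to the disposition page, yet the table as specified will not count them.

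At stake is a readable and complete count. A dose group could show zero in this table while its disposition data show a participant who left because of an AE. A reader would have to match listings to find out what the event was. The neighbouring AESI, SAE and MAAE tables would show the event, but nothing in their specification marks it as having led to discontinuation.

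**Working it through.** The plan states no figure on this point, so the check is mainly a comparison of windows.

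| Item | Source | Onset window |
|---|---|---|
| AESIs by SOC/PT | SAP 9.1.6 | Day 1-28 and Day 1-180 |
| SAEs by SOC/PT | SAP 9.1.7 | Day 1-28 and Day 1-180 |
| MAAEs by SOC/PT | SAP 9.1.8 | Day 1-28 and Day 1-180 |
| AEs leading to discontinuation by SOC/PT | SAP 9.1.10 | Day 1-28 only |
| Fatal AEs by SOC/PT | SAP 9.1.11 | Day 1-180 |

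**Three cases put through the rule in 9.1.10**

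1. AE with onset on Day 20, participant withdraws on Day 60. Onset is inside the window, so the case is counted.
2. AESI with onset on Day 60 that causes withdrawal. It is not counted in the 9.1.10 table. It does appear in the Day 1-180 AESI table, the 9.1.10 listing and the disposition data.
3. Nonserious AE that is neither an MAAE nor an AESI, with onset on Day 60. It lies outside the collection period, so the limit is set by collection and a wider table would not remove it.

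Only case 2 is a gap made by the table.

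**Calendar coverage**

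- Covered: 28/180 = 15.6% of follow-up.
- Not covered: 180 − 28 = 152 days; 152/180 = 84.4%.
- One omitted case in a planned dose group of 30: 1/30 = 3.3 percentage points.

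**Chance that the gap matters in practice**

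The formula is the one behind the detection probabilities in SAP 4.1, P(at least one) = 1 − (1 − r)^n. It reproduces the plan's figures: 1 − 0.95^30 = 78.5% and 1 − 0.90^30 = 95.8%.

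The documents give no rate r of discontinuation for an AE with onset after Day 28. The rates below are assumptions. They treat participants as independent and use the planned enrolment of 30 per dose group and 180 in total.

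| Assumed r | Expected cases, 180 × r | P(≥1) in a group of 30 | P(≥1) in 180 |
|---|---|---|---|
| 0.5% | 0.9 | 14% | 59% |
| 1% | 1.8 | 26% | 84% |
| 2% | 3.6 | 45% | 97% |
| 5% | 9.0 | 79% | >99% |

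SAP Section 12 says the study was closed early. If fewer than 180 were enrolled, or follow-up was shorter, these figures fall.

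**The case against.** The strongest defence is that Day 28 matches data collection. Day 1-28 is the only period in which every class of AE is recorded. SAEs, MAAEs and AESIs have Day 180 tables because they are collected to Day 180, so they are not an exact comparator for AEs of all kinds. A Day 1-180 column would mix full collection to Day 28 with restricted collection afterwards. This stands as a likely explanation, although the SAP does not give it, and it is a real drawback of the fix. It does not justify leaving out late SAEs, MAAEs and AESIs that cause withdrawal, because those are collected and linked.

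The second defence is that the cases are reported elsewhere. The listing has no onset limit, the disposition reasons include AE and death, late events are in their own Day 1-180 tables, and safety is judged by clinical review of all parameters. This also stands, and it limits the point to one table. A listing, however, gives no count or percentage by dose group, and a disposition reason gives no SOC or PT.

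Third, little depends on the table: AE discontinuation is not a primary endpoint, there is no hypothesis testing, and the holding rule on withdrawal after a Grade 3 AE (Protocol 5.9) is assessed by investigators continuously without it. That is correct and keeps the weight low.

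A reader might infer three stronger things that the documents do not support:

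- That withdrawals after Day 28 are dropped. The cut is on AE onset and not on the date of withdrawal.
- That late cases vanish from the safety reporting. They remain in the places named above.
- That 84% of the relevant events are lost. That figure is calendar time; most AE classes are not collected in that period, and no event rate is given.

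**Conclusion.** The point holds as a small reporting gap. The SOC/PT table in SAP 9.1.10 will not count a discontinuation caused by an SAE, MAAE or AESI with onset after Day 28, and no other planned table supplies that link. The number affected cannot be estimated from the documents and could be zero. Under assumed rates of 0.5% to 2%, at least one omitted case among 180 planned participants has a probability of 59% to 97%.

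The conclusion rests on two readings: that SAEs, MAAEs and AESIs are collected to the end of the study, as footnote m and the primary endpoint state, and that the table shells, which are not among the documents, add no second window. No primary result is affected.

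**What to change.** In SAP 9.1.10, add a Day 1-180 onset column beside the Day 1-28 column, in line with Sections 9.1.6 to 9.1.8. Footnote it to say that after Day 28 only SAEs, MAAEs and AESIs are collected, so the two columns do not rest on the same scope of collection.

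The cost is one column and one footnote, with no new data: the AE number on the disposition page already provides the link. The downside is the mixed collection scope in the wider column. The footnote discloses this but does not remove it.

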9.1.11. Death

The summary of AEs with an outcome of "Fatal" with onset date within day 1-180 will also be presented by SOC. The SOCs will presented alphabetically. Within each SOC, the PTs will be presented in alphabetical order.

All participants who have an AE with an outcome of "Death" will be presented in a listing by age group, dose group and participant number.

Deaths will be reported for both summaries and listings from the time participant signs the ICF until exit from study (up to day 180 after the study vaccine administration, day -180).

9.2. Clinical Laboratory Evaluations

The following laboratory assessments will be performed:

Hematology:	Basophils, eosinophils, erythrocytes (red blood cells), hemoglobin, leukocytes (white blood cells), lymphocytes, monocytes, neutrophils, and platelets
Chemistry:	Bilirubin (total and direct), alkaline phosphatase, alanine aminotransferase, aspartate aminotransferase, blood urea nitrogen, creatinine, and uric acid
SARS-CoV-2:	• SARS-CoV-2 serology (Ab), which will include S and N protein for prevaccination timepoints and N protein for postvaccination timepoints to monitor for undetected SARS-CoV-2 infections
	• SARS-CoV-2 RT-PCR (nasal swab)
HIV/HBV/HCV	• Hepatitis B surface antigen test
	• HIV 4 th generation antigen/Ab test
	• Anti-HCV test
Other analyses:	Female participants of childbearing potential:
	β -human chorionic gonadotropin (serum test at Screening; urine test at additional time points)
	Serum FSH, to confirm postmenopausal status (see protocol Section 13.2)

Individual safety laboratory measurements for hematology, chemistry and coagulation laboratory panel will be provided. All listings will include the age group, dose group, participant number, laboratory test name result, date and time of measurements, reference range, and flag for measurements that are outside the reference range and sorted by age group, dose group and participant number.

Laboratory abnormalities will be graded for severity using the FDA toxicity grading table (DHHS 2007). Clinically relevant laboratory abnormalities will be reported as AEs using the AE grading

A by-participant listing will be provided for pregnancy test by age group, dose group and participant number.

9.3. Vital Sign Measurements

Vital sign measurements will include systolic and diastolic blood pressure, oxygen saturation, pulse rate, respiratory rate, and body temperature. Observed values and changes from baseline will be summarized for each vital sign parameter by time point, and dose group.

A supporting by-participant listing of vital sign parameters along with the investigator assessment will be provided by age group, dose group and participant number.

9.4. Physical Examination

A complete physical examination including height and weight will be performed at Screening. Symptom-directed physical examinations will be performed as clinically indicated at subsequent visits. The results of the physical examination findings will be listed by participants and dose group, and sorted by age group, dose group and participant number.

9.5. Electrocardiogram

Not applicable.

10. Pharmacokinetics

Not applicable.

11. Pharmacodynamics

Not applicable.

12. Interim Analysis

A first interim analysis of safety and immunogenicity data covering at least neutralizing Ab titers against pseudovirus bearing S protein from ^{CCL} up to 14 days after study vaccine administration in participants enrolled in Cohorts 1, 2, and 3 will be performed including at least day 1 and day 15 data. A second interim analysis of safety and immunogenicity data covering at least neutralizing Ab titers against pseudovirus bearing S protein from ^{CCL} was planned, however this was cancelled as the study was closed early.

13. Changes in the Planned Analysis

Not applicable.

14. References

Department of Health and Human Services (DHHS), Food and Drug Administration, Center for Biologics Evaluation and Research (US). Guidance for industry. Toxicity grading scale for healthy adult and adolescent volunteers enrolled in preventative vaccine clinical trials. September 2007 [cited 2021 Jul 09]. Available from: https://www.fda.gov/media/73679/download

World Health Organization (WHO). WHO coronavirus (COVID-19) dashboard [Internet]. 2021 [cited 2021 Jul 07]. Available from: https://covid19.who.int/

15. Appendices

15.1. Schedule of Events

	Screening	D1	D2 ^a	D8	D15	D29	D85	D180 (EOS)	Early Termination Visit	Unscheduled Visit for Suspected COVID-19 ^b	Unscheduled COVID-19 Convalescent Visit ^e
Window	D-14 to -1	0	NA	±1	±3	±3	±5	±7	±7	NA	NA
Visit	1	2	NA	3	4	5	6	7	7	NA	NA
Informed consent	Х										
Inclusion/exclusion	Х										
Reassess study vaccine eligibility ^d		Х									
Demographics	Х										
Medical history (including vaccination history)	Х								Х	Х	Х
Treatment assignment		Х									
Pregnancy test ^c	Х	Х									
Clinical SARS-CoV-2 serology ^f	Х	Х					Х	Х	Х		
SARS-CoV-2 RT-PCR (nasal swab) ^g	Х	Х								Х	
Physical examination ^h	Х	Х		Х	X	Х	Х	Х	Х	Х	Х
Vital sign measurements ⁱ	Х	Х		Х	Х	Х	Х	Х	Х	Х	Х
Clinical safety laboratory tests ⁱ	Х	Х		Х							
Blood sample for binding IgG ^{f, k}		Х		Х	Х	Xi	Х	Х	Х		
Blood sample for neutralization ^{f, k}		Х		Х	Х	Xi	Х	Х	Х		
Blood for PBMC preparation for ICS (subset of participants)		Х			Х						
Vaccine administration		Х									
COVID-19 evaluation ^c											X ¹
Initiate eDiary for solicited AEs		Х									
Site staff review of eDiary			Х	Х							
Adverse events ^m	Х	Х	Х	Х	Х	Х	Х	Х	Х	Х	Х
Concomitant medication/vaccination	Х	Х	Х	Х	Х	Х	Х	Х	Х	Х	Х

Note: Due to the ongoing pandemic, safety follow-up visits may be completed via televisits, as permitted by country regulations. In-person visits

should be maintained in the study unless there is a public health emergency limiting access to study sites. During such an emergency, televisits can be employed to keep personal access to subjects and ascertain their safety at a high level.

a. A safety follow-up telephone call to each sentinel participant will be performed on Day 2 prior to the vaccination of the next participant.

b. Required for participants with suspected COVID-19.

c. Required for participants with confirmed COVID-19.

- d. Prior to study vaccine administration, participants will be reassessed for development of any new condition that would be considered exclusionary including acute illness, pregnancy, or development of new risk factors for severe COVID-19 illness. Assessment will be based on pregnancy test results, participant-reported symptomology, vital sign measurements, and physical examination findings. (Note: Sentinel participants will be required to remain at the study site for approximately 4 hours after study vaccination for observation.)
- e. WOCBP only: A serum pregnancy test will be performed at Screening. A urine pregnancy test by dipstick will be performed prior to study vaccination. Negative confirmation is required prior to study vaccine administration.
- f. Clinical SARS-CoV-2 serology testing will be performed at Screening and on D1 to confirm the serostatus of the participant and on D85 and D180 for detection of SARS-CoV-2 infection during the study. On D1, the serology sample should be collected *before* study vaccine administration. At baseline, D85, and D180 the serology analysis will include N protein to monitor for undetected SARS-CoV-2 infections. Binding IgG and neutralization will only be obtained at Day 85 and D180 in participants who did not receive a licensed or authorized COVID-19 vaccine after Day 29.
- g. SARS-CoV-2 nasopharyngeal or mid-turbinate swab for RT-PCR diagnostic testing will be performed at Screening for eligibility and Day 1 for analysis (result not required for eligibility). The screening sample for RT-PCR testing must be obtained and tested within the 7 days before Day1. Additional swabs may be taken at any visit (or between visits) as clinically indicated according to institutional practice.
- h. A complete physical examination including height and weight will be performed at Screening. Symptom-directed physical examinations will be performed as clinically indicated at subsequent visits.
- Vital sign measurements (temperature, pulse, respiration rate, and blood pressure) should be collected before and after study vaccination on D1.
 Vital sign measurements should also be performed before any scheduled blood collection. Participants who are febrile (temperature ≥38.0°C or ≥100.4°F) before study vaccination on D1 should be rescheduled for study vaccination within the relevant window period of Screening.
- j. Clinical safety laboratory testing will include hematology, serum chemistry, and coagulation. Screening laboratory tests may be repeated once for enrollment requirements. HIV 1/2, HB surface antigen, and anti-HCV testing will be performed at Screening only. Unscheduled visit may occur for the evaluation and follow-up of any AE. At unscheduled visits, clinical safety laboratory testing will be done as per investigator decision.
- k. Blood draws for immunogenicity assessments (binding IgG and neutralization) after D29 will only be obtained from participants who have not yet received a COVID-19 booster vaccination with an authorized or licensed product.
- 1. Participants will be instructed to inform the investigator in the event of a positive SARS-CoV-2 diagnostic test. In this case, he/she will be invited to perform an unscheduled visit on site for COVID-19 evaluation according to the definitions provided in protocol Section 6.6. All effort should be made by the investigator to ensure the disease assessment is performed in a timely manner versus the test results.
- m. Solicited local and systemic AEs will be collected during 7 days after study vaccination (Day 1 to 7) via eDiaries. Unsolicited AEs will be recorded for 28 days after study vaccination. SAEs, MAAEs, and AESIs will be collected for the duration of the study.

